11.1.5 Urgent Safety Measures

In accordance with the principles of GCP as laid out in ICH E6, the investigator(s) has/have primary responsibility for assuring subject safety throughout the performance of study procedures. An urgent safety measure is defined as any measure which an investigator may need to implement which is a deviation from, or a change in, the protocol to eliminate an immediate hazard(s) to trial subjects without prior IEC approval/favourable opinion.

The investigator may take appropriate urgent safety measures in order to protect the subjects of a clinical trial against any immediate hazards to their health or safety. However, the investigator must inform the Sponsor within 24 hours of having taken such measures.

The Sponsor in turn shall immediately, and in any event no later than 3 days from the date the measures are taken, give written notice to the licensing authority and the relevant IEC of the measures taken and the circumstances giving rise to those measures.

All urgent safety measures must be reported to the Medical Director using the contact information provided in Section 11.1.4 within 24 hours of having to take such a measure(s). Such reports can be initiated by telephone but must be officially documented by the investigator (by email) and must include details of what measures were taken and the circumstances giving rise to those measures. If there is an associated AE, this should be reported as described in Section 11.1.4.

GE Confidential Page 39 of 43

11.1.6 Pregnancy Reporting

This process is aimed at ensuring the appropriate monitoring of the potential risk related to study drug exposure of pregnant women and/or foetuses as well as the risks associated with exposure of a father, regarding congenital abnormalities or birth defects in their offspring. It also ensures compliance with applicable international and local regulations.

The requirements are applicable to all subjects following exposure to study drug.

Female trial subjects: The trial subject must be advised by the investigator to inform him/her immediately if she suspects she may be pregnant within 30 days after receiving VIZAMYLTM.

Male trial subjects: The trial subject must be advised by the investigator to inform him/her immediately if they suspect their partner became pregnant within 30 days after the subject was administered with study drug.

When a trial subject reports a pregnancy (post-study drug administration) to the investigator, a pregnancy test should be arranged for the trial subject (or their partner) by the investigator within 7 days of the pregnancy being reported.

The investigator must inform the Sponsor within 24 hours of receiving positive pregnancy test results using either a copy of the relevant eCRF page (demography or AE) or via email. The investigator should include an estimated date of conception when communicating with the Sponsor.

GE Confidential Page 40 of 43

12 PLANS FOR DISSEMINATING AND COMMUNICATING STUDY RESULTS

Annual progress reports will be submitted to the EMA.

The Sponsor will submit a final study report to the EMA PRAC within 12 months of the end of data collection or will submit a request for a waiver.

The Sponsor may submit the results of the study for publication in a peer-reviewed journal. Abstracts and/or oral presentations of the results at medical professional meetings may also be planned.

1 INTRODUCTION

The purpose of this Statistical Analysis Plan (SAP) is to provide detailed descriptions of the statistical methods, data derivations and data displays for study protocol GE067-027, 3.0 “A Post-Authorisation Safety Study to Evaluate the Effectiveness of VIZAMYL™ Reader Training in Europe” dated 11Dec2019 for final analysis. The table of contents and templates for the Tables, Figures and Listings (TFLs) will be produced in a separate document.

Any deviations from this SAP will be described and justified in the Clinical Study Report (CSR).

The preparation of this SAP based on International Conference on Harmonization (ICH) E6 and E9 guidelines.

All data analyses and generation of TFLs will be performed using SAS 9.3® or higher.

2 STUDY OBJECTIVES

2.1 Primary objective

The primary study objective is to assess the effectiveness of the VIZAMYL™ reader training programmes (in-person or electronic) in Europe by estimating the diagnostic accuracy, sensitivity, specificity, positive predictive value (PPV), and negative predictive value (NPV), of the visual interpretation of VIZAMYL™ images obtained in the course of clinical practice. Diagnostic accuracy is the overall true-interpretation rate for all subjects. One minus the diagnostic accuracy gives the overall image interpretation error rate.

At least 200 VIZAMYL™ images obtained in clinical practice will be reviewed (or will have been reviewed) by clinical readers recruited from European countries where VIZAMYL™ is commercially available [REDACTED]

[REDACTED]. The standard of truth (SOT) will be the majority blinded visual image interpretations of the same images by 5 independent expert readers.

2.2 Secondary objectives

Evaluate the impact of demographic and other factors (such as method of training, gap between training and reading, and country) on diagnostic accuracy to try to identify factors that may be associated with image interpretation errors.

Sensitivity is the true-positive (TP) image interpretation rate in subjects with brain amyloid. Specificity is the true-negative (TN) image interpretation rate in subjects without brain amyloid. Positive predictive value (PPV) is the TP image interpretation rate for subjects with positive VIZAMYL™ scans. Negative predictive value (NPV) is the TN image interpretation rate for subjects with negative VIZAMYL™ scans.

3 STUDY DESIGN

3.1 General study design

This is a non-interventional post-authorisation safety study (PASS) with the primary objective of assessing effectiveness of the VIZAMYL™ reader training programmes (in-person or electronic) in Europe by estimating the diagnostic accuracy of the visual interpretation of VIZAMYL™ images by clinical readers recruited from European countries where VIZAMYL™ is commercially available [REDACTED]

[REDACTED] (each reader will interpret (or will have interpreted) images collected at his/her institution, for a total of at least 200 images). The diagnostic accuracy of image interpretation will be determined across all images as well as for subsets of images by country and by reader. Sensitivity, specificity, PPV, and NPV will also be determined and will be reported as point estimates along with exact 95% confidence intervals (CIs). The SOT for classifying each image as correct (TP or TN) or incorrect (false positive or false negative) will be the majority blinded visual interpretations of 5 independent expert readers.

Imaging sites will be selected according to the criteria detailed in protocol section 9.2.2. Each imaging site will be assigned a 3-digit identifying number. The VIZAMYL™ images at each participating site will be obtained in clinical practice. Because VIZAMYL™ is approved and no longer investigational, the need for subject informed consent will be decided at each institution by the local independent ethics committee (IEC).

All subjects must satisfy all the inclusion criteria and none of the exclusion criteria as listed in the protocol. When required by the local IEC, signed and dated informed consent must be obtained from all subjects or the subject's legally acceptable representative, if applicable, in accordance with local regulations, prior to collection of any study-specific data. Each subject will be assigned a 7-digit identifying number; the first 3 digits will be the identifying number for the site at which the subject's VIZAMYL™ scan was obtained and the remaining 4 digits will be assigned consecutively at each site. Demographic data will be recorded for each subject.

The images will be de-identified (i.e., subject identifying information will be removed) so that inspection of an image will not reveal the identity of the subject from whom the image was obtained.

If anatomic images are used in the interpretation of the VIZAMYL™ images, they will also be de-identified and transmitted to the core image lab, and will be interpreted with the VIZAMYL™ images by the expert readers.

The clinical reader eligibility criteria are discussed in protocol section 9.2.4. Demographic data will be recorded for each clinical reader. Each clinical reader will be assigned an identifying letter that starts with C (for Clinical): CA, CB, CC, etc.

During the image interpretations, the clinical readers will not be (or were not) blinded to the subjects' clinical information, but will be blinded to the interpretations of the expert readers (which will not be available yet). Each clinical reader will interpret the VIZAMYL™ images

as they are collected at his/her site. VIZAMYL™ images will be interpreted as positive (significant levels of amyloid present) or negative (significant levels of amyloid absent) according to local practices at the institution; these classifications are consistent with the VIZAMYL™ reader training programme, the VIZAMYL™ Summary of Product Characteristics, and the European Association of Nuclear Medicine (EANM) guidelines on interpretation of amyloid positron emission tomography (PET) images. If anatomic images (Magnetic Resonance Imaging [MRI] and/or computed tomography [CT]) are available for a subject, the normal institutional clinical practice regarding use of these images in PET interpretation will be followed. The clinical reader will enter his/her interpretation and other data into an electronic case report form (eCRF). The site will remove identifying information (except for subject number) from the image and transmit the image electronically to the GE Healthcare image core lab.

The image core lab will assign a randomization code to the image and will remove the subject number.

The ≥ 200 images collected in this study will be interpreted separately by each of 5 expert readers, who will classify each image as positive or negative for brain amyloid. The expert readers will consist of 5 experienced nuclear medicine physicians or radiologists, with extensive experience in PET imaging (including amyloid imaging), who have completed a VIZAMYL™ training programme. The expert readers will be blinded to the subjects' clinical information and to the interpretations of the other expert readers and clinical readers, and will not be permitted to discuss images or interpretations with anyone. The expert read will result in at least $200 \times 5 = 1000$ expert blinded visual interpretations, which will be analysed by subject to determine the majority blinded visual interpretation, as follows. Each image will have 5 expert interpretations, each of which will be positive or negative. The image interpretation (positive or negative) made by the majority of the 5 expert readers will be taken as the majority interpretation. For example, if 3, 4, or 5 of the expert readers interpreted a specific subject's image as positive, then the majority interpretation for that image will be positive. The result of this analysis will be at least 200 majority interpretations (1 per image). The level of reader certainty will also be recorded on a scale of 1 to 5 (1 = lowest, 5 = highest).

Using subject number, each of the ≥ 200 clinical image interpretations will be matched to the corresponding expert reader majority interpretation for the subject and the image interpretation will be classified as a TP, TN, false positive (FP) or false negative (FN) using the expert reader majority interpretation as the SOT. For example, if an image interpretation is "positive" and the expert reader majority interpretation is "positive", the image interpretation would be classified a TP. If the expert reader majority interpretation were "negative", however, then the image interpretation would be classified as a FP. The numbers of TP, TN, FP, and FN images among the ≥ 200 original images will be used to calculate diagnostic accuracy:

$$\text{Diagnostic accuracy} = (\text{nTP} + \text{nTN}) / (\text{nTP} + \text{nTN} + \text{nFP} + \text{nFN})$$

Where nTP is the number of true-positive scans, nTN is the number of true-negative scans,

nFP is the number of false-positive scans, and nFN is the number of false-negative scans.

Sensitivity, specificity, PPV, and NPV will also be calculated:

$$\text{Sensitivity} = \text{nTP} / (\text{nTP} + \text{nFN})$$

$$\text{Specificity} = \text{nTN} / (\text{nTN} + \text{nFP})$$

$$\text{PPV} = \text{nTP} / (\text{nTP} + \text{nFP})$$

$$\text{NPV} = \text{nTN} / (\text{nTN} + \text{nFN})$$

Treatment-emergent adverse events (AEs) with onset or worsening between the start of VIZAMYL™ injection and subject discharge from the imaging suite will be recorded on an adverse event (AE) eCRF, along with the centre's assessment of relationship to VIZAMYL™, severity, seriousness, timing, need for treatment, and outcome.

Study procedures for prospective data collection are summarised in the Study Schedule of Events for Prospective Data Collection ([Table 3-1](#)). For collection of existing data, the activities in the “Subject Enrolment” and “Imaging Visit” columns in [Table 3-1](#) will have occurred in the past and may be obtained from the medical record, including whether or not the patient meets the inclusion and exclusion criteria.

Table 3-1 Study Schedule of Events for Prospective Data Collection

Procedures	Subject Enrolment	Imaging Visit	Post-Imaging	Responsible
Selection of imaging sites				Sponsor
Informed consent obtained from subject (if IEC requires)	X			Centre
Subject inclusion/exclusion criteria assessed	X			Centre
Subject demographic information recorded	X			Centre
VIZAMYL™ administration and PET imaging; AE monitoring from start of injection until discharge from imaging centre		X		Centre
Completion of electronic case report form			X	
De-identification of subject's images			X	Centre
Transmittal of subject's images to Sponsor image core lab			X	Centre
Preparation of images for expert readers			X	Sponsor

The image evaluation by expert readers will be prospective; these activities are summarised in [Table 3-2](#).

Table 3-2 Study Schedule of Events for Image Evaluation by Expert Readers

Procedures	Expert Selection	Expert Image Evaluation	Responsible
Identification of expert reader candidates	X		Sponsor
Informed consent obtained from expert reader candidates	X		Sponsor
Expert reader candidate inclusion/exclusion criteria assessed	X		Sponsor
Selection of 5 expert readers	X		Sponsor
Expert reader demographic information recorded	X		Sponsor
Independent review of images		X	Readers

3.2 Randomization and blinding

The image core lab will assign a randomization code to the image and will remove the subject number. The criteria for blinding are shown below in [Table 3-3](#).

Table 3-3 Blinding of Persons Involved in the Study

Personnel	Blinded To:
Subjects	Expert readers' image interpretations
Imaging Centre Site Personnel	Expert readers' image interpretations
Clinical Readers	Other clinical readers' image interpretations Expert readers' image interpretations
Expert Readers	Clinical readers' image interpretations Other expert readers' image interpretations Subject clinical information

3.3 Study treatments and assessments

Participating subjects will receive (or will have received) VIZAMYL™ intravenously prior to PET imaging, according to clinical practice.

Clinical readers may or may not have completed any training in reading VIZAMYL™ images, and some may have completed 1 or more VIZAMYL™ reader training programmes. They also may or may not have prior experience in reading VIZAMYL™ images.

Expert readers will have been trained in reading VIZAMYL™ images and will have experience in reading amyloid PET images.

4 STUDY ENDPOINTS

4.1 Primary endpoints

The primary endpoints are the diagnostic accuracy, sensitivity, specificity, PPV, and NPV across readers based on all evaluable images.

Using subject number, each of the ≥ 200 clinical image interpretations will be matched to the corresponding expert reader majority interpretation for the subject and the image interpretation will be classified as a TP, TN, FP or FN using the expert reader majority interpretation as the SOT.

4.2 Secondary endpoints

- The numbers and percentages of images for which 5 expert readers agree, 4 expert readers agree, and 3 expert readers agree.
- Estimates of diagnostic accuracy, sensitivity, specificity, PPV, and NPV by the following variables:
 - Country
 - Time from training to image interpretation (<6 months, ≥ 6 months)
 - Specialty of the reader
 - Training method (s) used by the clinical reader (in-person, electronic, or both)
 - Number of scans read by the clinical reader in practice prior to the study (<50, ≥ 50)
 - Reader classification certainty (1 to 5)
- Safety Endpoint:- Adverse events (AEs)

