7 RATIONALE AND BACKGROUND

Neuropathological diagnostic criteria for Alzheimer's disease (AD) include whether or not there are neuritic plaques in the brain, and if so, their relative frequency [Khachaturian, 1985]; [Mirra et al. 1991]; [NIA-Reagan, 1997]. Plaques can be found in aged cognitively normal subjects, so although plaques are necessary for a diagnosis of AD, they are not sufficient (neurofibrillary tangles must also be present). On the other hand, the *absence* of significant levels of amyloid plaques in the brain is sufficient to rule out AD.

Positron emission tomography (PET) imaging using VIZAMYLTM, Flutemetamol (¹⁸F) Injection, is a method to detect abnormal neuritic plaque density. Flutemetamol (¹⁸F), the active ingredient, is an analogue of Pittsburgh Compound B (PiB; 2-[4-methylamino phenyl]-1, 3-benzothiazol-6-ol) radiolabelled with the positron-emitting isotope ¹⁸F. Both flutemetamol and PiB are neutral analogues of Thioflavin T, an accepted histological stain for detecting neuritic plaques. PiB was designed to cross the blood-brain barrier, bind to neuritic plaques with high affinity at low nanomolar concentrations, and clear rapidly from normal brain tissue. The PET imaging properties of PiB derive from the positron-emitting isotope, carbon-11 (¹¹C), which has a radioactive half-life of 20 minutes, too short for commercial distribution. The longer radioactive half-life of fluorine-18 (110 minutes) permits fluorine-labelled PET amyloid imaging agents such as VIZAMYLTM to be distributed commercially, offering more flexibility in scheduling of PET imaging. Visual interpretation of flutemetamol (¹⁸F) PET images has high sensitivity and specificity for the *in vivo* detection of abnormal brain neuritic plaque density in the brain.

VIZAMYLTM was approved by the United States FDA 25 October 2013 and by the EMA 22 August 2014. VIZAMYLTM is a radiopharmaceutical medicinal product indicated for PET imaging of β-amyloid neuritic plaque density in the brains of adult patients with cognitive impairment who are being evaluated for AD and other causes of cognitive impairment. VIZAMYLTM is for diagnostic use only and should be used in conjunction with clinical evaluation. Owing to its radioactive nature and consequent short shelf-life, VIZAMYLTM is manufactured on demand in response to a valid prescription.

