8 RESEARCH QUESTIONS AND OBJECTIVES

The research question to be answered by this study is: *How effective is the VIZAMYL*TM reader training programme in clinical practice in Europe? To answer this question, the study has the following primary and secondary objectives.

Primary:

The primary study objective is to assess the effectiveness of the VIZAMYLTM reader training programmes (in-person or electronic) in Europe by estimating the diagnostic accuracy, sensitivity, specificity, PPV, and NPV, of the visual interpretation of VIZAMYLTM images obtained in the course of clinical practice. Diagnostic accuracy is the overall true-interpretation rate for all subjects. One minus the diagnostic accuracy gives the overall image interpretation error rate.

Secondary:

The secondary study objective is:

Evaluate the impact of demographic and other factors (such as method of training, gap between training and reading, and country) on diagnostic accuracy to try to identify factors that may be associated with image interpretation errors.

Sensitivity is the true-positive (TP) image interpretation rate in subjects with brain amyloid. Specificity is the true-negative (TN) image interpretation rate in subjects without brain amyloid. Positive predictive value (PPV) is the TP image interpretation rate for subjects with positive VIZAMYLTM scans. Negative predictive value (NPV) is the TN image interpretation rate for subjects with negative VIZAMYLTM scans.

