9.3 Variables

9.3.1 **Demographic Data**

The demographic data listed in Table 5 will be collected about subjects and readers. In addition, every effort will be made to collect these data from readers who decline to participate as well.

Table 5 **Demographic Data to Be Collected**

| Group | Demographic Factors | | |
|------------------|---|--|--|
| Subjects | • Age | | |
| | • Gender | | |
| | • Race | | |
| | Reason for scan | | |
| | • Country | | |
| | Imaging centre | | |
| | Type of medical practice of referring physician (primary, secondary, tertiary) | | |
| | VIZAMYL™ dose in MBq or mCi | | |
| | Type of anatomic images available, if any (MRI and/or CT) | | |
| Clinical readers | • Age | | |
| | • Gender | | |
| | • Race | | |
| | • Country | | |
| | • Institution | | |
| | VIZAMYL TM reading training status | | |
| | • VIZAMYL TM reading training method (electronic, in-person, or both) | | |
| | • Date(s) of VIZAMYL TM reading training (this will be used to determine the time from | | |
| | last training to the date of image interpretation) | | |
| | Training with other amyloid PET imaging agents | | |

[figure not shown]

Table 5 Demographic Data to Be Collected

| Group | Demographic Factors |
|-------|---|
| | Medical specialty |
| | Years of experience reading PET images |
| | Number of brain PET scans read in clinical practice |
| | Type of medical practice (primary, secondary, tertiary) |
| | • Prior experience (clinical or research) with any amyloid PET imaging agent (including |
| | VIZAMYL TM) |

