The efficacy clinical reader population will consist of each clinical reader who has interpreted the images included from his/her institution and has had their image interpretations classified as TP, TN, FP, or FN through comparison with the SOT (the expert reader majority interpretation).

Page 29 of 43

Subject Demographics/Other Baseline Characteristics

A table will be provided with the following information:

- Number of subjects enrolled.
- Number of subjects in the safety population.
- Number of subjects with VIZAMYLTM images included in the efficacy analysis.

GE-067-027 C

Version 7.0 Approved

Demographic information (Table 5 above) will be summarised using descriptive statistics.

Study Treatments

All subjects will have received VIZAMYLTM as part of routine clinical practice. The dose and volume administered will be summarised across all subjects.

Clinical Reader Demographics/Other Baseline Characteristics

A table will be provided with the following information:

- Number of clinical readers participating.
- Number of clinical readers' image interpretations included in the efficacy analysis.

Demographic information (Table 5 above) will be summarised using descriptive statistics. Demographic information will be reported for readers who are randomly chosen to participate as well as the complete pool of potential readers who agreed to participate in addition to readers who decided not to participate where data are available.

Primary Analysis

The primary analysis will be the determination of diagnostic accuracy, sensitivity, specificity, PPV, and NPV across readers based on all evaluable images (at least 200 images) (point estimates and exact 95% CIs).

Secondary Analyses

The numbers and percentages of images for which 5 expert readers agree, 4 expert readers agree, and 3 expert readers agree will be summarised. In addition, results will be analysed by the following variables:

- Country
- Time from training to image interpretation (<6 months, >6 months)
- Specialty of the reader
- Training method(s) used by the clinical reader (in-person, electronic, or both)

- Number of scans read by the clinical reader in practice prior to the study (<50, >50)
- Reader classification certainty (1 to 5)

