8.4.2 Clinical Reader - demographic and baseline characteristics

Continuous demographic variable clinical reader's age will be summarised descriptively, and the following categorical demographic and baseline variables will be summarised using counts and percentages. Summaries will be based on the efficacy clinical reader population.

- Gender
- Race
- Country

Baseline characteristics:

- VIZAMYL™ reading training status
- Number of times training done (1, 2, ≥ 3)
- VIZAMYL™ reading training method (electronic, in-person, or both)
- Training with other amyloid PET imaging agents
- Medical specialty
- Time (month) from last training to the date of image interpretation (<6 months, ≥ 6 months)
- Number of brain PET scans read in clinical practice (<50, ≥ 50)
- Type of medical practice (primary, secondary, tertiary)
- Prior experience (clinical or research) with any amyloid PET imaging agent (including VIZAMYL™)

In addition, the following continuous baseline characteristics will be summarised descriptively:

- Duration (months) from last training to the date of image interpretation
- Years of experience reading PET images
- Number of brain PET scans read in clinical practice
- Years of experience reading PET images

- Number of times training done

Listings will be provided for each clinical reader's demographic and baseline characteristics.

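### Accuracy is compared across the training-to-reading gap by a single cut at 6 months, so any change after 6 months is averaged into one figure although the gap in months is already to be derived

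*SAP*

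**What the plan says.** The objective in Protocol 8 is to study factors "such as method of training, gap between training and reading, and country" for their effect on diagnostic accuracy. SAP 2.2 repeats it: "Evaluate the impact of demographic and other factors (such as method of training, gap between training and reading, and country) on diagnostic accuracy".

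The accuracy analyses of the gap all use one variable, "Time from training to image interpretation", in two classes:

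- Protocol 9.7, secondary analyses: "Time from training to image interpretation (<6 months, >6 months"
- SAP 4.2: "Time from training to image interpretation (<6 months, ≥ 6 months"
- SAP 8.6.3: the same two classes as SAP 4.2, reported for prospective, retrospective and pooled images.

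The protocol's version leaves a gap of exactly 6 months in neither class; the SAP's version closes that hole.

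The exact gap is available. Protocol Table 5 collects training dates and says of them: "this will be used to determine the time from" last training to interpretation. SAP 8.4.2 summarises "Duration (months) from last training to the date of image interpretation" as a continuous reader characteristic. Neither document relates that continuous value to whether a read was correct. Neither states a maximum gap, and existing reads may be used with no limit on age (Protocol 9.4.1).

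**The concern.** In a study of training effectiveness, the practical question behind this factor is whether accuracy holds as training recedes. A lower class next to training and an open upper class answer only part of it. A reader 7 months after training and one several years after it contribute to the same percentage. If accuracy is stable for a time and then declines, or declines steadily, the planned table shows one averaged figure for everything from 6 months on, and a user of the report could not tell which happened or how low the late reads fell. The information needed to look further is already in the data set.

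**Working it through.** **Step 1. The plan's own precision figures.** The exact (Clopper-Pearson) limits at 90% accuracy, from beta quantiles with x = 0.9n, are BETA(0.025; x, n−x+1) and BETA(0.975; x+1, n−x). They give widths of 24.4, 20.9, 18.5 and 16.7 points at n = 30, 40, 50 and 60, as in Protocol Table 6 and SAP Table 5-1. They also give 26.4 points at n = 26 and 37.0 at n = 14, as stated in the text. At n = 200 the interval is 85.0% to 93.8%, width 8.8 points, which meets the stated target of less than 10%. The documents give no figure for the gap classes.

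**Step 2. How wide the upper class could be.** The product was approved "by the EMA 22 August 2014" (Protocol 7), and the protocol is dated 11 December 2019. That is 1,937 days: 1,937 / 30.4375 = 63.6 months, or 1,937 / 365.25 = 5.3 years. This is the gap at the protocol date for a reader trained at approval with no later training. It is an inference from two dates; the documents report no gaps.

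**Step 3. Illustration of what the cut averages.** Assumptions, none from the documents except the 200 images: gaps spread evenly over 0 to 64 months, and two hypothetical courses of accuracy.

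- Course A falls in a straight line from 95% to 80%: accuracy at month g is 95 − 15g/64.
- Course B stays at 95% to month 24, then falls in a straight line to 75% at month 64: 95 − 20(g − 24)/40.

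On a straight segment, the mean in a band is the value at its midpoint. Image counts are 200 × band length / 64.

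| Gap (months) | Images | Course A | Course B |
|---|---|---|---|
| <6 (planned) | 19 | 94.3% | 95.0% |
| ≥6 (planned) | 181 | 86.8% | 88.1% |
| 6 to <24 | 56 | 91.5% | 95.0% |
| 24 to <60 | 112 | 85.2% | 86.0% |
| ≥60 | 13 | 80.5% | 76.0% |

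For example, the ≥6 figure is 95 − 15 × 35/64 = 86.8 in course A and (18 × 95 + 36 × 86 + 4 × 76)/58 = 88.1 in course B. The planned table shows a drop of 7.5 points for A and 6.9 for B. The two courses look alike there, yet B has no decline at all in the first two years.

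**Step 4. Precision of the planned classes and of finer bands.** At 90% accuracy the exact interval is 67.5% to 98.9% (31.3 points) for 19 images and 84.7% to 94.0% (9.3 points) for 181. Widths are 17.4 points for 56 images, 12.0 for 112 and 38.5 for 13. Sensitivity and specificity would be thinner still: at the plan's 65% SOT-positive, 19 images contain 19 × 0.35 ≈ 7 negatives, and 6 correct of 7 gives 42.1% to 99.6%.

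**Step 5. Precision of a single trend.** Under course A the slope is −15/64 × 12 = −2.8 points per year. Mean accuracy is 87.5%, and the standard deviation of the gap is (64/12)/√12 = 1.54 years. Treating images as independent, the standard error is about √(0.875 × 0.125) / (√200 × 1.54) = 0.0152, a 95% half-width of about 3.0 points per year. Clustering by reader would widen this: the 7.5% cap requires only 1/0.075 = 13.3, that is 14, readers.

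**The case against.** The strongest reply is that the study is descriptive, with no tests, and that the objective only asks to try to identify factors. The 6-month split delivers two estimates with intervals, and no other secondary factor is modelled. The remaining pieces are also reported: reader characteristics are listed (SAP 8.4.2), accuracy by reader is tabulated (SAP 5) and image-level reads are listed (SAP 8.6.2). All of this is true, but these outputs leave the reader to assemble the relation, and the SAP does not commit to showing it. A slope with an interval is an estimate, so the absence of tests does not rule it out.

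Three stronger readings are tempting and not supported:

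- A reader might infer that loss of skill over time cannot be seen at all. In both illustrated courses the planned table shows a drop of about 7 points. What is lost is the course after 6 months.
- A reader might infer that gaps do exceed five years. The documents do not say so. The gap runs from the last training, so retraining shortens it; existing reads may have short gaps; and the data-collection dates are not shown.
- A reader might set the 7.5-point contrast in course A against the 15-point fall and conclude that half the effect is hidden. These are not like for like: one is a difference between class means, the other a difference between two instants, which no banded table would return.

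It also stands that finer bands are no cure in themselves. With a top band of ≥24 months, 40/64 = 62.5% of the illustrated images would still be pooled. Time since training may also be confounded with accumulated reading experience, so no unadjusted trend can isolate loss of skill.

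**Conclusion.** The point holds as a cheap improvement to a secondary analysis. The planned analysis reports a contrast at 6 months and averages everything later, although the gap in months is to be derived. How much this hides depends on the distribution of gaps and the course of accuracy, both unknown. In the illustration, a single figure of 86.8% to 88.1% stands for band means that run from 91.5% to 80.5% (course A) or from 95.0% to 76.0% (course B). Those values rest wholly on the assumed even spread and assumed declines. If most gaps are short, or accuracy is stable, little is hidden. The primary analysis and the stated sample-size figures are unaffected.

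**What to change.** Keep the 6-month split. Add to Protocol 9.7 and SAP 8.6.3 one descriptive estimate, pooled over prospective and retrospective images: the change in the proportion of correct reads per year since last training, using the gap in months computed for each image, with a 95% confidence interval that allows for clustering by reader. Restrict it to trained readers, since SAP 3.3 admits readers with no training and they have no gap. Define the gap per image in SAP 7.1 (now marked as not applicable), counting from the last training completed before that read.

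Optionally add a plot of accuracy against the gap, or accuracy alone (not sensitivity and specificity) in a few bands that also divide the later period, with cut-points set from the observed gaps before image unblinding.

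The cost is SAP and protocol wording and one table; no new data are needed. The estimate will be imprecise, with possibly as few as 14 readers, and may be confounded with experience. It should be reported as exploratory and not as proof of skill loss.
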